## **A. Protocol Abstract**

The proposed project is a multi-site collaboration focused on implementing improved standards for conducting computed tomography (CT) with respect to the doses used to obtain these examinations; studying strategies to implement these standards across diverse healthcare facilities using a cluster randomized, stepped-wedge design; and then more broadly disseminating the strategies based on what was learned in the implementation trial; and conducting an observational study of dissemination during years 4-5. The broad goal of this work is to improve the safety of CT by lowering the doses to which patients are exposed and thus reduce the number of cancers that result from these exposures. This project is focused on determining the best approaches to accomplish this. We will study the change process itself as it varies across different types of healthcare facilities with varying organizational structures to understand the best strategies to adapt our interventions based on context and other factors to improve its chances of success. This project will be conducted in partnership with diverse healthcare delivery institutions in the U.S., Asia, and Europe. All participating institutions have: Radimetrics installed, a Bayer Health software product for radiation dose monitoring; identified a site leader who is an institutional champion for change; and demonstrated an organizational commitment to dose optimization.

## **B. Background and Significance**

Despite how frequently CT is used (75 million CT examinations are conducted annually in the U.S.) and the high doses of radiation it delivers (up to 500 times higher than a chest x-ray), there are few standards for the conduct of CT examinations. This has resulted in excessive variation in the doses that patients receive when they undergo CT, and the routine use of doses higher than needed for medical diagnoses – doses associated with an increased risk of cancer. Several recent studies have confirmed an elevated risk of cancer associated with exposure to CT. Although there has been increasing attention paid to CT use from consumer advocates, medical groups, quality organizations, and state and national legislators around improving the safety of medical imaging, little progress has been made: our recent research documents that radiation

doses remain higher than needed for diagnosis. The manufacturers are developing lower dose devices, but these will not replace existing machines for decades or longer as over 10,000 machines are currently in operation. Thus, current machines need to be made safer.

No U.S. professional or governmental organization is responsible for collecting, monitoring, or reporting patient dose information for CT, and no comprehensive standards or guidelines cover conduct of CT studies. The general principle is that doses should be "as low as reasonably achievable," but no guidelines define reasonable or achievable. In the absence of explicit guidelines, practice variation potentially introduces unnecessary harm from excessive radiation and a practice climate in which almost any dose is acceptable. The FDA issued a national advisory for hospitals to carefully check their CT protocols after patients received brain radiation doses approximately 1000-times higher than the average dose for brain CT. One hospital reported "intentionally" using high doses to get clearer images, highlighting the lack of standards. The absence of guidelines on radiation dosing in the U.S. contrasts with quality assurance programs in Europe that have been in place for more than a decade. European programs use diagnostic reference levels that help facilities identify when their average doses are too high. These programs define upper limits for radiation dose that should be exceeded only for justified reasons documented in medical records. The UK has had CT mandates for more than 15 years, with extensive radiation dose monitoring at institutional, local, and national levels. However, concrete benchmarks have been created even in the UK for only a few routine imaging protocols and have not been updated since 2003, generating interest in standardizing and optimizing CT radiation doses across a range of indications and protocols. This study will draw on the UK experience and collect data on a large number of CT indications with a goal of creating benchmarks covering a larger proportion of protocols and practices.

Diverse organizations agree that patients must receive the lowest radiation dose possible to achieve the necessary medical benefit from CT. Organizations such as the American College of Radiology, the Institute of Medicine (IOM), the Center for Medicare and Medicaid Services, the Joint Commission on Health Care Accreditation, U.S. Congress, and the Image Gently social marketing campaign for children all stress safer CT practices. Recognizing

the potential risks of dose variation and radiation overdosing, the FDA plans to increase oversight of CT and called for institutions and professional societies to create diagnostic reference levels that, if exceeded, would trigger investigative action and dose-reduction strategies. Achieving safer CT also requires more quality information on current radiation exposures—data that we collect in a related, PCORI sponsored project. The next step is generating, applying, and evaluating validated dose-lowering and optimizing strategies across diverse healthcare institutions—the goal of this proposal.

Concrete data are needed on successful strategies to lower and optimize CT radiation doses. This will require balancing the importance of CT to clinical care with the risk of radiation injury from medical errors and the potential of elevated cancer risk even when protocols are followed. The first step is lowering CT doses when feasible. Evidence suggests average CT doses could be reduced by 50% or more without reducing diagnostic accuracy. In this project, we will leverage the expertise of nationally respected scientists and radiation physicists to assess and reduce CT doses at facilities and standardize and optimize protocols across participating organizations. We will compare different strategies in a clustered randomized controlled trial (RCT) of implementation using a stepped-wedge design and work closely with our partner organizations to study and implement lasting and sustainable changes to improve CT safety.

## **C. Study Objectives**

### **C.1 Primary Objective:**

- Using a stepped-wedge cluster randomized controlled trial (RCT), evaluate the effects of a simple audit and of a tailored multicomponent intervention on lowering facility-level radiation doses from diagnostic CT imaging, relative to baseline, for head, chest, and abdomen/pelvis CT. We will randomize facilities based on time zone and independence of facilities within their associated healthcare organizations.
  - Primary outcome: Effective dose

## **C.2 Secondary Objectives:**

- (1) Evaluate the effects of a simple audit and a multicomponent intervention on lowering facility-level radiation doses using additional dose metrics, including CTDIvol (Computed Tomography Volumetric Dose Index) and DLP (Dose Length Product).
  - Outcomes: CTDIvol, DLP
- (2) Evaluate the delayed and/or longer-term effects of the two interventions on effective dose, CTDIvol and DLP.
- (3) Identify facilitators and barriers (assessed through surveys of participating facilities) associated with successful and failed implementation of dose optimization (i.e., improvements in doses after each intervention). This will be assessed following completion of the simple audit, multicomponent intervention, and one year following the multicomponent intervention.
  - Outcomes: Effective dose

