### **H.1 Included Patients and CT Examinations**

We will include consecutive patients who undergo a diagnostic CT at a participating facility from November 2015 to December 2018. We will include CT scans of the head, chest, and

abdomen and pelvis. As an exploratory analysis, we will also evaluate combined chest/abdomen/pelvis (CAP) exams.

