### 3. Delayed effects: Effective dose, CTDIvol, DLP

Time frame (see Section M for details):

Baseline 1: 9-12 months prior to simple audit;

Follow-up 1: 3-6 months following 4 weeks washout after simple audit;

Baseline 2: 2-6 months prior to multicomponent intervention;

Follow-up 2 : 3-6 months following 2 weeks washout after multicomponent intervention;

Follow-up 3 : 12-15 months after multicomponent intervention

Within each anatomic area, the mean effective dose and the proportion of CT scans with an effective dose over the benchmark during Follow-up period 3 will be compared to doses during the Baseline periods prior to each intervention and the Follow up periods after each intervention.

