## **L. Study Arms (Tracks)**

The study will divide facility clusters into three separate tracks. Each facility will first receive the simple audit, followed later by the multicomponent intervention, and will be staggered as to when they begin each intervention. Two of the three randomized tracks will be invited to participate in an in-person meeting, which will be timed to coincide with the audit for one of

the tracks and to coincide with the multicomponent intervention for one of the tracks. The third track will serve as a control (i.e., no in-person meeting). This will permit assessing whether the in-person meeting enhances the impact of the audit and/or multicomponent intervention.

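### Objective C.2(2) promises longer-term effects of both interventions, but the only late window follows both, so the audit's effect after the multicomponent start is not identifiable

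*Combined protocol and SAP*

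**What the plan says.** Section C.2, objective (2), covers both interventions: "Evaluate the delayed and/or longer-term effects of the two interventions on effective dose, CTDIvol and DLP".

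Section L fixes the order for all facilities: "Each facility will first receive the simple audit, followed later by the multicomponent intervention, and will be staggered as to when they begin each intervention". There is no track that stays on the audit alone.

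Section K, Secondary Analysis item 3 (Delayed effects), lists five windows, four of which matter here. The audit phase is measured from "Baseline 1: 9-12 months prior to simple audit" and then, once the audit has been delivered, in "Follow-up 1: 3-6 months following 4 weeks washout after simple audit". The second phase has its own reference window, given as "Baseline 2: 2-6 months prior to multicomponent intervention". The late window is "Follow-up 3 : 12-15 months after multicomponent intervention". The planned comparison sets Follow-up 3 against the baselines and follow-ups of both interventions.

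Sections M.1 and N.1 describe the same late window, tied to the multicomponent intervention; M.1 counts it from completion of that intervention. N.1 puts all periods into the model for the multicomponent phase and compares the post-intervention period with both baselines.

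Section H.1 limits the data to patients who "undergo a diagnostic CT at a participating facility from November 2015 to December 2018".

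**The concern.** Section D.1 asks whether a simple, inexpensive audit does as well as the intensive intervention. Whether the audit's effect fades, holds or grows bears directly on that choice, and objective (2) promises an answer for each intervention.

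The analysis supplies one late window, and by then every facility has also had the more detailed feedback, the tailored recommendations and the invitation to eight weekly calls described in Section L.2. If the Follow-up 3 contrasts with Baseline 1 or Follow-up 1 were read as evidence on the audit, they could credit it with durability that the second intervention produced, or hide the fact that its effect had faded.

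**Working it through.** **1. What the Follow-up 3 contrasts estimate.** Take all quantities as net of the time trend. Let A1 be the audit effect at Follow-up 1, A3 the audit effect remaining at Follow-up 3, and M3 the effect added by the multicomponent intervention at Follow-up 3.

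- Follow-up 3 minus Baseline 1 = A3 + M3
- Follow-up 3 minus Follow-up 1 = A3 + M3 − A1

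A3 and M3 enter only as a sum. An audit that has faded completely (A3 = 0, M3 = −d) and a fully durable audit with nothing added (A3 = −d, M3 = 0) give identical values in both lines. Controlling for time, as N.1 plans, removes secular drift but does not split the sum, because no facility contributes Follow-up 3 data without the multicomponent intervention.

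**2. Where the audit can be seen alone.** Follow-up 1 and Baseline 2 both lie after the audit and before the multicomponent intervention. Baseline 2 minus Baseline 1 and Baseline 2 minus Follow-up 1 are therefore audit-only contrasts. Baseline 2 is in the time frame of the delayed-effects analysis and in the all-periods model, but neither K nor N.1 names either contrast as a follow-up of the audit.

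**3. How long the audit-only interval is.** The text states no figure, so there is none to reproduce. The inputs are the windows in Section K, the eight weekly calls in L.2 and the dates in H.1. The month ranges are read as lengths; 4 weeks is 0.9 months and 8 weeks is 1.8 months.

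From the windows:

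- Follow-up 1 ends 0.9 + 3 = 3.9 to 0.9 + 6 = 6.9 months after the audit.
- If Baseline 2 starts only after Follow-up 1 ends, the interval is 3.9 + 2 = 5.9 to 6.9 + 6 = 12.9 months.
- If the two windows overlap as far as possible, the interval is the longer of the two: 3.9 to 6.9 months.

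Together this gives roughly 4 to 13 months.

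From the data window: November 2015 to December 2018 inclusive is 2 + 3 × 12 = 38 months. Suppose a facility uses all of it, from the start of Baseline 1 to the end of Follow-up 3 at month 15. The longest possible interval is then 38 − Baseline 1 − 15, less the calls if Follow-up 3 is counted from their completion.

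| Baseline 1 | Follow-up 3 counted from multicomponent start | Follow-up 3 counted from end of calls |
|---|---|---|
| 9 months | 38 − 9 − 15 = 14 | 14 − 1.8 = 12.2 |
| 12 months | 38 − 12 − 15 = 11 | 11 − 1.8 = 9.2 |

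Reading Baseline 1 instead as the span from 12 to 9 months before the audit also gives 38 − 12 − 15 = 11. The cap is therefore about 9 to 14 months.

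**The case against.** The best defence is that the plan is not silent on the audit. The objective is worded to allow delayed or longer-term effects and sets no horizon for the audit. Baseline 2 is listed under delayed effects and is in the model, so Baseline 2 versus Baseline 1 needs no new data. Nor does Section K call Follow-up 3 versus Follow-up 1 a delayed audit effect; it only names the windows to be compared. All of this stands, and it makes any misattribution a risk of interpretation rather than something the authors have written. It does not close the gap, because a contrast that could be taken from the model is not a prespecified one, and every delayed contrast that is specified uses Follow-up 3.

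Three stronger readings are tempting, and the documents do not support them.

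- A reader might infer that every facility moves on within a year of its audit. The text gives no interval, N.1 says period lengths differ by intervention and track, and the timeline graph (M.1, R.6) is not in the text available for review. The cap reaches 14 months on the loosest count.
- A reader might infer that no facility could supply any audit-only data in months 12 to 15. A window complete to month 15 does not fit any of the counts above, but months 12 to 14 could fit the loosest.
- A reader might infer that the audit's longer-term effect cannot be observed at all. Baseline 2 gives a view of it up to the multicomponent start.

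It is also fair to object that Follow-up 1 and Baseline 2 may overlap, leaving few or no later audit-only scans in some tracks. The fix has to allow for that.

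**Conclusion.** The concern holds in limited form. Follow-up 3 versus Baseline 1 or Follow-up 1 measures the longer-term effect of the full sequence. The audit's effect after the multicomponent start is not identifiable, and as written the plan does not answer the audit half of objective (2). This follows from the order of the interventions and does not depend on the length of the interval between them.

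The audit-only horizon is roughly 4 to 13 months from the stated windows, with a cap of about 9 to 14 months. Those figures assume that the month ranges are lengths (apart from the alternative Baseline 1 reading shown), and the cap also assumes that Follow-up 3 runs to month 15 within the H.1 dates. Any Baseline 2 contrast also relies on the model in N.1 handling the time trend adequately. The primary analysis of each intervention is not affected.

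**What to change.** - In C.2(2) and in Section K, Delayed effects, describe Follow-up 3 versus Baseline 1 and versus Follow-up 1 as the longer-term effect of the audit followed by the multicomponent intervention.
- For the audit, prespecify two delayed contrasts from the all-periods model: Baseline 2 versus Baseline 1, and Baseline 2 versus Follow-up 1. Use only Baseline 2 scans dated after Follow-up 1 ends.
- State the months since audit covered by those scans in each track. Where a track has none, report no delayed audit estimate for it.
- Limit the audit conclusion to the period before the multicomponent intervention starts.

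The cost is revised wording and two contrasts on data already planned, with no new collection and no change to the interventions. The downside is a shorter and less precise longer-term claim for the audit.

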## **D. Research Design and Methods**

### **D.1 Study Design**

We will conduct a pragmatic stratified randomized controlled trial (RCT) of two interventions using a two-phase stepped-wedge design. We will first evaluate the effect of a single-component intervention (simple audit). Second, we will evaluate the effect of a multicomponent intervention (audit + tailored recommendations + quality improvement collaborative calls combined with Change/Implementation Team support) with considerable external support and a close relationship with the University of California leadership team, but local flexibility. We will also assess whether participation in an in-person meeting (where education in quality improvement is emphasized) enhances the impact of the audit and/or the multicomponent intervention. We will determine if the simple, inexpensive audit and feedback approach is as effective as the intensive, multicomponent intervention at reducing facility-level mean radiation dose or the percentage of examinations with doses above the benchmark compared to baseline. Since audit with feedback is expected to be only weakly effective, we will implement it first. The

second intervention will give tailored feedback on needed changes plus guidance using quality improvement methods that facilitate organizational change.

A total of 116 facilities from one of 20 parent institutions will participate in the trial. The individual facilities will be the unit of comparison in the trial. However, in order to ensure that facilities that are highly integrated with each other (for example, share staff and management) do not get randomized to separate groups (which would be impractical to implement and lead to complete cross over) we assessed the relative independence of each facility so that we can keep interdependent facilities in the same randomized units (which in some cases will include more than one facility). Thus, the unit of comparison is the individual facility, whereas the unit of randomization is the facility cluster (see G below). This resulted in 84 units (facility clusters) to be randomized.

The 84 facility clusters will be randomly divided into three tracks, which will undergo the audit and multicomponent intervention in a staggered fashion. In addition to this, one of the three randomization tracks will be invited to participate in the in-person meeting (where focused education on quality improvement and strategies for dose optimization will be provided) to coincide with provision of the simple audit, and one randomization track will be invited to the in-person meeting to coincide with the multicomponent intervention. By offering participation in the in-person meeting at different times in relation to the audit and multicomponent intervention, we will assess whether the in-person meeting enhances the impact of each intervention on outcomes.

For our secondary outcomes focused on assessing factors associated with optimization in dose, a mixed-methods approach with interviews and surveys will determine factors and strategies associated with successful implementation. Surveys will combine material from existing validated surveys (such as the Change Process Capability Questionnaire (CPCQ)) adapted to radiology-specific quality improvement to measure organizational priority and readiness for change, and from the Physician Practice Connections–Readiness Survey (PPC-RS) to measure implementation changes over time.

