We will also compare the multicomponent intervention and simple audit effects to determine which is more effective. We will also compare how participation in the in-person meeting impacts the effects of the simple audit and multicomponent intervention by including interactions with an effect of in-person meeting and the particular intervention. Each facility will act as its own control, and we will control for underlying time trends, which are estimable because of the stepped-wedge design.

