## **O. Sample Size**

Statistical power depends on between-class coefficient of variation (standard deviation between facilities divided by average prevalence per facility). Based on prior research, we expect these values to vary between 0.4 and 1.1, depending on anatomical region and response metric. With 84 unique clusters, reflecting 116 facilities, to be randomized and at least 27-28 scans per facility for each anatomical region and age group (adult/children), in each measurement period, we will have an 80% power to detect a change of 5 percentage points (from 25% to 20%) in percentage of examinations with doses above the benchmark after the intervention versus baseline, using a two-sided significance level of 5%. The exceptions to this are children's head scans, which only require 15 scans per facility in each measurement period to achieve the same power with 84 clusters. We expect each facility to contribute, on average, at least 60 scans per day. With each measurement period being at least 1 month it is very likely 80% power will be surpassed. The effect of multicomponent intervention is expected to be greater than the effect of auditing; thus, the same sample size would also be sufficient in detecting the significance of multicomponent intervention.

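### The plan promises to establish whether the audit is equally effective, but provides only a comparison for difference, with no margin or confidence-interval criterion

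*Combined protocol and SAP*

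**What the plan says.** Section D.1 sets the question: "We will determine if the simple, inexpensive audit and feedback approach is as effective as the intensive, multicomponent intervention", judged on facility mean dose or on the percentage of examinations above the benchmark. Section N.1 supplies the analysis: "We will also compare the multicomponent intervention and simple audit effects to determine which is more effective". Neither section, nor any other, gives an equivalence or non-inferiority margin, a confidence-interval criterion, or a rule for what a non-significant result means.

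The primary objective in C.1 is to "evaluate the effects of a simple audit and of a tailored multicomponent intervention on lowering facility-level radiation doses" relative to baseline. The comparison of the two interventions with each other is not among the objectives in C.1 and C.2, nor among the planned analyses in Section K.

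Section O says "we will have an 80% power to detect a change of 5 percentage points (from 25% to 20"%) after the intervention versus baseline, "using a two-sided significance level of 5"%. It then argues that the same size suffices for the multicomponent intervention because its effect should be larger. It gives no power or precision for the contrast between the two.

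**The concern.** D.1 asks an equivalence or non-inferiority question: can the inexpensive option stand in for the intensive one? N.1 answers a different question, namely whether one effect exceeds the other. Without a margin, neither possible result settles D.1. A non-significant difference may mean that the effects are close, or only that the contrast is imprecise. A significant difference may be too small to matter, because registry data can bring very many scans.

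At stake is whether the trial can support a statement that the audit alone is enough. This would hold even if the fixed order of the two interventions caused no difficulty, because it concerns what may be concluded from the comparison.

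**Working it through.** **Inputs from Section O.** Two-sided 5% level; 80% power for 25% to 20%; 84 clusters; 27-28 scans per facility, region, age group and period as the planning minimum; at least 60 scans per facility per day on average; periods of at least one month. For the between-facility coefficient of variation (CV), "we expect these values to vary between 0.4 and 1.1, depending on anatomical region and response metric".

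**Assumed here.** Three equal tracks of 28 clusters; differences of 2.5 and 5 points, since the plan defines no relevant difference; the period layouts, since the timeline figure was not available.

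**1. Section O's own figure.** I used a stepped-wedge model with fixed period effects, a cluster random effect with SD = CV × p, and sampling variance p(1−p)/n. With three tracks and three periods, 80% power for 5 points needs n = 24 to 31 over CV 0.4 to 1.1. It gives 27 at CV 0.4 with p = 0.25, and 27-28 at CV 0.6 to 0.8 with p = 0.225 (the midpoint of 25% and 20%). With four periods it is 21 to 25. The stated 27-28 is plausible. It cannot be uniquely reproduced because the CV, layout and formula are not given.

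**2. Precision that Section O implies at the minimum.** SE = 5/(1.960 + 0.842) = 1.785 points for one before-after contrast. The audit-versus-multicomponent contrast depends on its definition:
- Follow-up 2 minus Follow-up 1, both effects taken from Baseline 1: a single contrast, factor 1.
- Difference of two separate before-after changes: factor √2.
- The same, if Follow-up 1 and Baseline 2 were the same scans: factor √3.

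Power = Φ(d/SE − 1.96) + Φ(−d/SE − 1.96).

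| Factor | SE (points) | 95% half-width | Power, 2.5 points | Power, 5 points |
|---|---|---|---|---|
| 1 | 1.785 | 3.5 | 29% | 80% |
| √2 | 2.52 | 4.9 | 17% | 51% |
| √3 | 3.09 | 6.1 | 13% | 37% |

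**3. A model closer to N.1.** N.1 puts all periods in one model, so step 2 is only a rough guide. I fitted both effects jointly with common period effects (5 to 8 periods). I also allowed an extra cluster-by-period SD, which stands for facilities moving differently over time. The documents give no value for it. The expected volume is 60 × 30 = 1,800 scans per facility per month, before splitting by region and age.

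| Scans per cluster-period | Cluster-by-period SD (assumed) | Power, 2.5 points | Power, 5 points |
|---|---|---|---|
| 28 | 0 | 32-41% | 84-93% |
| 60 | 0 | 58-71% | above 99% |
| 300 or 1,800 | 0 | above 99% | above 99% |
| 1,800 | 5 points | 62-75% | above 99% |
| 1,800 | 10 points | 21-28% | 65-78% |

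At high volume, power for 2.5 points is governed almost entirely by a quantity that the plan does not state.

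**4. The opposite risk.** With no cluster-by-period variation, the SE shrinks as 1/√n. At 1,800 scans the factor-1 SE is 1.785 × √(27.5/1,800) = 0.22 points, so a true difference of 2.80 × 0.22 = 0.6 points has 80% power. With an even split over three regions (600 scans), the SE is 0.38 and the corresponding difference 1.1 points. The plan does not say whether differences that small would count against equal effectiveness.

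**The case against.** Four points can fairly be made for the plan.

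First, nothing in it says that a non-significant difference will be read as equal effectiveness. A reader might infer this from D.1, but N.1 describes an ordinary comparison of effects and leaves the meaning of a null result undefined. Section O's 5% level is also stated for the comparison with baseline, not for this contrast. This objection stands.

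Second, a reader might infer from the table in step 2 that the design usually misses a relevant difference. The documents do not support that. They define no relevant difference, Section O treats 27-28 scans as a minimum and expects far more, and the √2 and √3 factors do not represent the all-periods model. In the joint model at the expected volume, power for 2.5 points falls below 50% only under the assumed SD of 10 points. This also stands, with a limit: the favourable figures need facilities to change almost in step, and the protocol expects otherwise. Section L.2 foresees some facilities resisting change, Section G expects responses to vary with facility culture, and C.2 studies successful against failed implementation. Small facilities also have less data. Section E admits those with 120 scans in three months, about 40 per region if split evenly over three.

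Third, the contrast is not a listed objective, and Sections D.1 and O expect the audit to be the weaker option. Equal effectiveness is thus not the working hypothesis, which limits the weight of the point. It does not remove the explicit undertaking in D.1.

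Fourth, a 2.5-point margin is the reviewer's example and says nothing about mean effective dose. That is accepted, and the fix asks for separate margins.

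**Conclusion.** The point holds as a mismatch between the stated question and the stated analysis. D.1 promises a finding on equal effectiveness; N.1 offers only a comparison of which effect is larger, without a margin or interval criterion; Section O sizes the trial only for each intervention against baseline. A non-significant difference would therefore not answer D.1, and at very large scan counts a significant one might not either.

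The frequency of either outcome cannot be fixed from the documents. Power for an assumed 2.5-point difference runs from about 20% to above 99%, depending on scan volume, on how the contrast is formed and, at the expected volume, chiefly on between-facility variation in change. These figures rest on assumed layouts and differences and cover only the percentage above benchmark. For mean effective dose the plan gives no SD, so nothing can be calculated. The primary comparisons with baseline are not affected.

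**What to change.** **D.1.** Replace the undertaking to determine equal effectiveness with: *estimate the difference in effect between the audit and the multicomponent intervention, with a 95% confidence interval.*

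**N.1.** Add: *A non-significant difference will be reported as inconclusive. The audit will be described as equally effective only if the 95% confidence interval for the additional reduction from the multicomponent intervention lies wholly below a margin fixed before analysis. The margin will be set separately for the percentage of examinations above benchmark and for mean effective dose.* State which periods form the contrast, since its precision depends on this. A margin of 2.5 points (half of Section O's effect) is an illustration only; the investigators must choose and justify the values.

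**Cost.** Wording in two sections and agreement on two margins; no new data. The trial may be unable to claim equal effectiveness. If the true difference were zero, the chance of meeting the criterion is Φ(margin/SE − 1.96). At Section O's planning minimum this is 12% to 29% for a 2.5-point margin and 37% to 80% for a 5-point margin, over the three factors in step 2. With more scans and little between-facility variation in change it would be higher.
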